**STUDY SYNOPSIS**

Study Title	Phase IIb trial of Recombinant Novel Coronavirus Vaccine (Adenovirus Type 5 Vector) (Ad5-nCoV) in adults 18 years of age and older, living with HIV.
Full Title	A phase IIb clinical trial to evaluate the efficacy, safety and immunogenicity of two doses of Recombinant Novel Coronavirus Vaccine (Adenovirus Type 5 Vector) in adults 18 years of age and older, living with HIV.
Objectives	
Primary Safety Objectives:
 

• Evaluate the incidence of solicited adverse reactions within 7 days after vaccination.

• Evaluate the incidence of unsolicited adverse events within 28 days after vaccination.

• Evaluate the HIV viral load 24 and 52 weeks after vaccination

• Evaluate the incidence of serious adverse events (SAE) and medically attended adverse events (MAE) within 52 weeks after vaccination in all participants.

 
Primary Immunogenicity Objectives:
 

• Evaluate the seroconversion rate of S-RBD IgG antibody on Day 28, Day 84 and Week 24 and Week 52 after vaccination, measured by ELISA.

• Evaluate the immunogenicity of two doses of the vaccine.

 
Secondary Safety Objectives:
 

• Evaluate the incidence of a decrease in CD4+ cell count by <math>\geq 20\%</math> at 24 and 52 weeks after vaccination.

• Evaluate changes in the CD4/CD8 ratio at 24 and 52 weeks compared to the basal value.

• To evaluate the efficacy of two doses of Ad5-nCoV in different age groups from 14 and 28 days to 24 and 52 weeks after vaccination. This will be evaluated by weekly participant contact to assess for any signs or symptoms of COVID 19.

 
Secondary Immunogenicity Objectives:
 

• Evaluate the GMT of S-RBD IgG antibody on Day 28, Day 84 and Week 24 and Week 52 after vaccination, measured by ELISA.

• Evaluate the GMI of S-RBD IgG antibody on Day 28, Day 84 and Week 24 and Week 52 after vaccination, measured by ELISA.

• Evaluate the seroconversion rate of pseudo-virus neutralizing antibody on Day 28, Day 84 and Week 24 and Week 52 after vaccination.

• Evaluate the GMT of pseudo-virus neutralizing antibody on Day 28, Day 84 and Week 24 and Week 52 after vaccination.

• Evaluate the GMI of pseudo-virus neutralizing antibody on Day 28, Day 84 and Week 24 and Week 52 after vaccination.

- Evaluate the positive rate and level of IFN- $\gamma$ , TNF, IL-4, IL-5, IL-13 stimulated by peptide pool of S protein on Day 28, Day 84 and Weeks 24 and Week 52 after vaccination, measured by intracellular cytokine staining (ICS) (in a subset of approximately 50 participants).

### Exploratory Objectives

- To evaluate the efficacy of two doses of Ad5-nCoV in preventing virologically confirmed (PCR positive) COVID-19 disease occurring 14 days and 28 days to 52 weeks after vaccination, regardless of severity.
- To evaluate the efficacy of two doses of Ad5-nCoV in preventing virologically (PCR) or serologically (four-fold increase in SARS-CoV-2 anti-N IgG from pre-immunization to post symptom, defined as Day 21-28 post illness blood test, or pre-symptom to post-symptom blood test) confirmed COVID-19 disease occurring 14 and 28 days to 52 weeks after vaccination, regardless of severity.
- To evaluate the efficacy of two doses of Ad5-nCoV in preventing severe COVID-19 disease caused by SARS-CoV-2 infection from 14 and 28 days to 24 and 52 weeks after vaccination.

*Severe disease is defined as: 1) Clinical signs at rest indicative of severe systemic illness (respiratory rate  $\geq 30$  per minute, heart rate  $\geq 125$  per minute,  $SpO_2 \leq 93\%$  on room air at sea level or  $PaO_2/FiO_2 < 300$  mm Hg), 2) Respiratory failure (defined as needing high-flow oxygen, non-invasive ventilation, mechanical ventilation or ECMO), 3) Evidence of shock ( $SBP < 90$  mm Hg,  $DBP < 60$  mm Hg, or requiring vasopressors), 4) Significant acute renal, hepatic, or neurologic dysfunction, 5) Admission to an ICU*

- Evaluate the efficacy of Ad5-nCoV in preventing asymptomatic disease of COVID-19 (confirmed by N IgG antibody on week 52 after vaccination).
- Evaluate the severity of COVID-19 cases among vaccine recipients (based on WHO or FDA criteria) as compared to the control group, to measure antibody-mediated disease enhancement (ADE).
- Evaluate for any evidence of SARS-CoV-2 virus shedding in COVID-19 cases that occurred 28 days to 52 weeks after vaccination (detection of viral nucleic acid every 2 days after being confirmed).
- Perform genotyping of SARS-CoV-2 virus isolates of COVID-19 cases that occurred 28 days to 52 weeks after vaccination.
- Evaluate incidence of suspected but unconfirmed cases of COVID-19 (either because of negative or no tests).

Indication	Prevention of novel coronavirus disease (COVID-19) caused by infection with the SARS-CoV-2 coronavirus.
Target population	Generally healthy adults 18 years of age and older, living with HIV

Sample Size	N=500
Rationale for study	
The 2019 novel coronavirus (SARS-CoV-2) is a positive non-segment single-stranded RNA virus, belonging to the Coronaviridae family of Nidovirales. There are six known coronaviruses in humans, including 229E and NL63 in the alpha genus, OC43 and HKU1 in the beta genus, Middle East respiratory syndrome-associated coronavirus (MERS-CoV), and severe acute respiratory syndrome-associated coronavirus (SARS-CoV).
 
The coronavirus isolated from the lower respiratory tract of patients with unexplained pneumonia in Wuhan is a new type of genus <math>\beta</math> coronavirus. Following the outbreak of severe acute respiratory syndrome coronavirus (SARS-CoV) in 2002 and the outbreak of MERS-CoV in 2012, SARS-CoV-2 is the third highly pathogenic coronavirus. The Coronavirus Disease 2019 (COVID-19) is caused by the infection of the 2019 novel coronavirus (SARS-CoV-2) started in January 2020. World Health Organization (WHO) declared COVID-19 a worldwide pandemic on March 12, 2020. As of Oct.20, 2020, there were over 42 million cases worldwide and over 1 million deaths in 185 countries/regions [1]. China had reported 87,028 confirmed cases, the US has over 8 million cases, and Canada over 200,000 cases [1]. As of November 28, 2020, there were over 61.8 million cases worldwide and over 1.4 million deaths in 185 countries/regions [1]. The COVID-19 pandemic has brought heavy economic pressure, medical burden, and severe harm to people's lives and health.
 
It is necessary and very urgent to develop preventive vaccines against COVID-19 to meet the global needs.
 
The vaccine candidate Ad5-nCoV, intended to prevent the COVID-19 caused by SARS-CoV-2, is jointly developed by CanSino Biologics Inc. and its collaborator, the Beijing Institute of Biotechnology. Using the replication-deficient human adenovirus type 5 as a vector, Ad5-nCoV has been developed through recombinant virus construction, amplification, cell culture, purification, and formulation. Ad5-nCoV expresses the specific S protein of SARS-CoV-2. It is suggested that both humoral and cellular immune responses play an important role in protective immunity according to the results of pre-clinical, phase I, and phase II studies conducted by CanSino Biologics. This study is a phase IIb clinical trial to evaluate the efficacy, safety, immunogenicity of two doses of Ad5-nCoV at a dose level of <math>5 \times 10^{10}</math> vp in healthy adults, aged 18 years of age and older living with HIV.

Testing Vaccine	
Study Product: Ad5-nCoV manufactured by CanSino Biologics Inc.
 
Active Ingredients: Replication-defective recombinant human type 5 adenovirus expressing S protein of novel coronavirus
 
Excipients: Mannitol, sucrose, sodium chloride, magnesium chloride, polysorbate 80, HEPES, and glycerin
 
Packaging: The vaccine is contained in a vial
 
Specification: 0.5 mL/vial
 
Dosage: <math>5 \times 10^{10}</math> vp (<math>\geq 4 \times 10^{10}</math> vp)

	
Shelf Life: Tentatively 24 months
 
Storage: It is recommended to store and transport at 2-8 °C (details of the temperature requirements are specified in the pharmacy manual).
 
Administration: Intramuscular (IM) injection in the deltoid muscle of the upper arm.
 
Schedule: A double-dose of vaccine is scheduled for all participants. A second dose of vaccine is scheduled for all participants at Day 56.
 
Developers: CanSino Biologics Inc. Beijing Institute of Biotechnology
 
Manufacturer: CanSino Biologics Inc.

Study design	
Summary: This Phase IIb study is a clinical trial for 500 participants 18 years of age or older living with HIV. All participants will receive two doses of the study vaccine and will be followed to monitor vaccine candidate safety, immunogenicity, and efficacy during 52 weeks. Fifty five days after the first vaccination, all participants will receive a second injection.
 
Study Interventions:
 
All participants will be subject to the following procedures:
 

Informed consent The signed informed consent must be obtained before study participation.

Check inclusion and exclusion criteria All inclusion and exclusion criteria will be checked at the screening in-person visit.

Collect demographic data and participant contact information. Record participant's demographic data such as date of birth, sex, gender, height, weight and race in the participant's eCRF. A current email addresses and or phone numbers will be collected for each participant. Contact information may also be used to remind participants of up-coming in-person visits.

Medical history Obtain the participant's medical history by interview and/or review of the participant's medical records and record any pre-existing conditions or signs and/or symptoms present in a participant prior to the first study injection in the eCRF. This will include reviewing any health condition that may prevent the participant from enrolling in the study, such as an unstable health condition. HIV clinical, treatment, and laboratory history will be reviewed.

HIV status, viral load, CD4 and CD8 counts At screening visit, HIV status will be verified based on a previous serologic result or previous detectable viral load. HIV status can also be confirmed with a prescription for antiretroviral treatment or a follow-up record from your treating physician. Viral load, and CD4 and CD8 counts samples will be collected at the first screening/baseline visit, randomization visit, and

	
week 24 and week 52 visits. Screening visit value will be used as reference value for comparison with further values.
 

Check contraindications, warnings and precautions to injection Contraindications, warnings and precautions to injection must be checked at the beginning of the First Injection Visit.

Urine Pregnancy Test/Birth Control Women of child-bearing age will be asked to perform a urine pregnancy test before the Injection Visits. The result of the urine pregnancy test must be negative in order to proceed with vaccine administration. In addition, participants who are able to become pregnant or could impregnate a partner are required to have used approved contraception for least 30 days prior to the study vaccination, and commit to use it for 90 days after the study vaccination.

Screening conclusion Participants will be deemed eligible to participate upon reviewing medical history and inclusion and exclusion criteria. This will occur prior to vaccination on First Injection Visit and will be verified before Second Injection.

Assess pre-injection vital signs (body temperature, blood pressure, pulse rate and respiratory rate) The body temperature of all participants needs to be measured prior to any study product administration on First and Second Injection Visits. Body temperature may be measured by any method (oral, axillary). If the participant has fever (fever is defined as temperature <math>\geq 38.0^{\circ}\text{C}</math> orally or <math>\geq 37.8^{\circ}\text{C}</math> axillary) on the day of injection, the injection will be rescheduled within 1 week.

Check and record prior medications and concomitant medication/injection Prior medications and concomitant medication/injection must be checked and recorded in the eCRF. Prior medications should include any medication taken by the participant within 14 days prior to screening. Participants will be asked to avoid over-the-counter medications such as antipyretics (e.g., acetaminophen) and anti-inflammatory medications (e.g., ibuprofen, naproxen) in the 12 hours before study vaccine receipt but will be allowed to take these over-the-counter medications as needed to treat fever or other AE after vaccination. Usage of these over-the-counter medications will be recorded as concomitant medications and linked to the AE collected as solicited or unsolicited events, as the case may be.

Check and record intercurrent medical conditions Any medical conditions should be collected in the clinical chart and recorded in the eCRF.

Baseline serology Approximately 25 mL of whole blood will be collected from each participant at First Injection Visit, Day 28, Day 84, week 24 and week 52 and separated for serum. The serum will be aliquoted. The results of antibody testing from baseline serum will not be used to determine eligibility for enrolment; instead, results will solely be used for analysis and comparison purposes. Presence of pre-existing SARS-CoV-2 antibodies found in baseline serum will be used for a stratified immunogenicity and efficacy sub-analysis. The second aliquot will be

--	--

	
stored as a back-up. For participants who entered in the blinded version and then were unblinded and vaccinated, baseline serology will not be performed again, taking the values from the baseline visit performed at the first visit.
 

• For linking purposes, each participant will be assigned a treatment identification number. The number of each administered treatments must be recorded in the eCRF.

• Injection of study vaccine After completing all prerequisite procedures prior to injection, one dose of the assigned vaccine will be administered IM in the deltoid muscle, preferable of the non-dominant arm. If the investigator or delegate determines that the participant's health on the day of administration temporarily precludes administration, the visit will be rescheduled within 1 week. There will be a 15-minute wait after each vaccination to monitor for any rare anaphylactic reaction. At Day 56 after first vaccination, all participants will get a second injection of the investigational vaccine (Second Injection Visit)

• Safety participant contacts Every 4 Weeks for 52 weeks there will be telephone calls following vaccination. They will be used to continuously collect any SAE and MAE data. Participants can report any AE they experience at any time during the study period; however, only SAE and MAE will be entered into the eCRF. In-person visits will occur for Day 28 visit (to collect solicited and unsolicited events, Day 56 (Second Injection Visit), Day 84 and Week 24, and Week 52 visits.

• Efficacy participant contacts All participants will have efficacy participant contacts weekly, for 52 weeks following vaccination. There will be approximately 52 efficacy participant contacts. All efficacy participant contacts will be emails, although other methods such as phone calls or text messages, if preferred, are acceptable. Each participant contact needs to be recorded in the study electronic case report form. The purpose of these participant contacts is to ask if the participants had any symptoms of illness they may be experiencing, regardless of severity. Any possible COVID-19 relevant symptoms will trigger laboratory testing for SARS-CoV-2 infection.

• Illness participant contact visits (Confirmed or suspected infection during study) Participants will be provided detailed instructions regarding the signs and symptoms of COVID-19 disease at each participant contact and will be instructed to seek medical attention and notify study staff should symptoms occur. Symptoms of interest include fever, cough, difficulty breathing, diarrhea, nausea, vomiting, prolonged fatigue, respiratory symptoms, chills, myalgia, sore throat, headache, congested/runny nose, pneumonia, difficulty swallowing, anosmia/ageusia (loss of sense of smell/taste), and neurological events. During the observation period of the study, if any of these symptoms develop in a participant, he/she should immediately follow local procedures for care of suspected COVID-19 illness and contact the study team. If a COVID-19 infection is found during the study, a case investigation will be undertaken according to locally recommended procedures.

--	---

- If COVID-19 is suspected, the participant will have a nasopharyngeal/throat swab taken. Testing for COVID-19 by PCR will be performed at the local clinical laboratory.
- If negative, the test will be repeated in 3 days from the first testing day.
- All attempts will be made to re-test positive samples in a reference laboratory. If the local lab is also a reference laboratory, then a confirmatory sample is not required.
- If the PCR is positive, nasopharyngeal/throat swabs will be taken every 2 days times 3 and then weekly and tested for COVID-19 by PCR until a negative sample is obtained.
- A serum sample (10mL blood) will be collected at the time of illness presentation and testing for SARS-CoV-2 anti-N IgG antibodies will be performed at Nexelis Laboratories (Canada).
- At Day 21-28 post-illness, a second serum sample will be taken and sent to the central laboratory for anti-N IgG.
- Participants who were PCR negative will also have that visit on day 21-28, where they will be tested for SARS-CoV-2 antibodies (Nexelis Laboratories (Canada)). This visit takes place at the research site where the participant is enrolled.
- Participants who develop COVID-19 infection post-vaccination will be carefully monitored for vaccine-related disease enhancement in collaboration with their primary physician who will be encouraged to obtain specimens in accordance with the Brighton Collaboration definition (Munoz, 2020), including a serum sample tested locally for C-reactive protein (CRP), ferritin, and procalcitonin, biomarkers that have been associated with predicting more severe disease outcome in infected patients.

Participants who develop COVID-19 disease will continue to be followed for other study outcomes by telephone while in isolation, and at the study site once recovered and released from isolation by public health officials.

- **Final serology**

Approximately 25mL of whole blood will be collected and will then be separated into serum at week 52. The serum will be aliquoted. The first aliquot will measure anti-N IgG antibodies, at the Nexelis Laboratories (Canada). The second aliquot will be stored as a back-up. The one-year antibody levels measured against anti-N IgG antibodies will be compared to the participant's baseline levels to evaluate the exploratory efficacy analysis against asymptomatic infection.

- **E-diary and Diary Cards**

Participants will be provided with access to an e-diary and a thermometer, and instructions about how to use them. A paper diary card may be available if required by the study site. Participants will be asked to record solicited AE for 7 days after receiving the vaccination, and unsolicited AE for 28 days in their diary. A second e-diary or a paper diary will be provided at Day 56 and will be collected at Day 84 visit. The completed e-diary and diary cards will be reviewed and data collected at the 28-Day safety in-person visit. Non completion of the e-diary

	
or diary cards will be investigated with the participant through telephone call(s) or any other convenient procedure. All data collected from the e-diary and diary cards will be uploaded into the eCRF.
 

● Immunogenicity in-person visit

1. Blood collection for ELISA and pseudo-virus neutralization antibody measurement
Approximately 25mL of whole blood will be collected on First Injection Visit, Day 28, Day 84, Week 24, and Week 52, as described above. These in-person visits will occur at the participant's local study site. Serum will be separated into two aliquots. A baseline antibody titer against SARS-CoV-2 will be established from the blood sample collected on First Injection Visit, as outlined in the "baseline serology" description. In addition, these samples will also be used to evaluate for additional immunogenicity objectives including: the seroconversion rate of S-RBD IgG antibody, GMT of S-RBD IgG antibody, GMI of S-RBD IgG antibody, seroconversion rate of pseudo-virus neutralizing antibody, GMT of pseudo-virus neutralizing antibody, and the GMI of pseudo-virus neutralizing antibody at Day 28, Day 84, Week 24, and Week 52. The second aliquot will be stored as a back-up.

2. Blood collection for ICS measurement
In a subset of approximately 50 participants, approximately 30mL of whole blood will be collected. Collections will occur on First Injection Visit (baseline), just prior to vaccination, and on Day 28, Day 84, and at 24 and 52 weeks post-vaccination. TNF, IL-4, IL-5, IL-13 will be measured by ICS on Day 28, Day 84 and Weeks 24 and 52 after vaccination. PBMC will be shipped on liquid nitrogen to Nexelis Laboratories (Canada).

Visit plan	
All participants will have at least 6 (six) planned in-person visits on Screening visit/First Injection Visit and Day 28, Day 56 (Second Injection Visit), Day 84, Week 24, and Week 52. The Screening/baseline visit will entail reviewing the ICF, completing a medical history of the participant, reviewing inclusion and exclusion criteria, and collecting a blood sample for HIV viral load and CD4/CD8 counts. A baseline SARS-CoV-19 antibody (Nexelis Laboratories), and a urine pregnancy test in women of child-bearing potential will be performed. The vaccine will be administered after having the negative result on the pregnancy test. Participants are required to remain at the study site for a minimum of 15 minutes after receiving the vaccine to monitor for any vaccine-related AE.
 
Participants will be given access to an e-diary or paper diary card to record solicited AE from First Injection Visit- day 7 and unsolicited AE from First Injection Visit- day 28. The data in the completed e-diary or diary card will be reviewed and data will be collected on Day 28.

	
A new e-diary or paper diary card to record solicited and unsolicited AE from Second Injection will be provided at Second Injection Visit- Day 56. The data in the completed e-diary or diary card provided during the Day-56 visit will be reviewed and data will be collected at visit on Day 84. Further details are outlined in Section 3.7 and 5.1.
 
All participants will be contacted on a weekly basis to be reminded to report any signs or symptoms of illness to study staff. Participants will either be contacted by the site weekly, or they will receive an automated message (email) with a link to answer questions about whether or not they had an SAE, an MAE or COVID-19 symptoms. Participants will also be asked on their day 7 contact about any events that might meet a pause or early termination criterion. The reporting and monitoring of any participant illness are consistent with meeting the primary efficacy objective. If a participant becomes ill, they will be asked to immediately proceed to the site designated by their local study team where they will be assessed and treated as deemed appropriate. Participants will also receive a telephone call every 4 weeks, to evaluate for the incidence of any SAE or MAE.
 
A subset of 50 participants will have additional immunologic testing performed, following the same visit schedule, to evaluate T-cell response to the Ad5-nCoV vaccine.
 
If a participant demonstrates signs or symptoms of illness, an unplanned in-person visit may occur for evaluation and possible treatment. If, for any reason following an electronic participant contact, the investigator would like to conduct an in-person visit (at home or at the site) with a participant, they may do so at their discretion.

Pause and early termination	
Study Suspension Criteria
 
If a suspension criterion is met, the study will be put on hold, and further injections will not occur until a safety review has been conducted. Should a suspension criterion be met, the local PI will inform the PIs, Sponsors, and NRA within 24 hours.
 
Suspension criteria includes:
 
Grade 3 or greater AE occurring in >15% of participants will constitute study suspension criteria. To be included as suspension criteria, AE must begin within three days after study injection (day of injection and 2 subsequent days) and persist at Grade <math>\geq 3</math> on three consecutive days, depending upon symptom severity and kinetics.
 
A suspected, unexpected serious adverse reaction (SUSAR) that is life-threatening or results in death will warrant study suspension.
 
Other study suspension criteria include if the IDMC assessed the potential safety risks to be harmful, or if the vaccine candidate might be ineffective.
 
Study Early Termination Criteria
 

• Required by the sponsor, or

- Required by the regulatory authority, or
- Required by an institutional review board (IRB)

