In its original version, the protocol limited inclusion to "people living with HIV on stable treatment and virologically suppressed..." .

Likewise, the design was double-blind versus placebo in a 2:1 ratio.

The advancement of the national vaccination reduced the possibilities of access to the study under such design, for which this protocol amendment was proposed.

Volunteers initially included in the study will receive two doses of the vaccine and will continue their follow-up as established in the protocol.

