#### 3.2 Study Groups

A total of 500 participants will be enrolled to receive the vaccine. All participants will be monitored for solicited adverse events for 7 days, unsolicited adverse events for 28 days, SAEs and MAEs for the one year duration of the study, and antibody measurements at baseline, Day 28, Day 84, week 24, and week 52. A subset of 50 participants will have cellular immunity measured at those same intervals.

This protocol amendment provides for unblinding of participants who were entered into the study in the double-blind schedule. For participants who entered the double-blind schedule, the visit process will be as follows:

a) Sites will receive an unblinding list detailing participants who received placebo or study vaccine. Participants who received placebo will be invited to continue in the study under the

open-label study scheme and should make visits from V1.B (first vaccine) onwards, after signing the informed consent, completing visits on day 28 (V2.B), day 56 (second dose) (V3.B), day 84 (V4.B), week 24 (V5.B) and week 52 (V6.B). In this group of participants already enrolled, no antibody dosage collection will be performed at the V1B visit; the V1 values at study entry will be taken. The letter B is added to the visits to differentiate this group of participants who must reorganize the schedule of visits from the administration of the first dose of CoVID vaccine after the unblinding. The procedures for this group are detailed in Table 2.

b) Participants who, after the unblinding, are found to have received study vaccine at the initial visit, will complete the visits established by protocol together with the administration of dose 2 of the study (day 56) onwards, after signing the informed consent. In this group of participants there will be no changes in the nomenclature of the visits.

For both arms (placebo and study vaccine), efficacy contacts are restarted with the second injection visit.

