### Recording of prior and concomitant medications/products and concomitant administration

The following prior and concomitant medications/products/vaccines must be recorded in the eCRF if administered during the indicated recording period:

- All concomitant medications/products, except vitamins and dietary supplements, administered from 14 days prior to screening up to 28 days following any dose of study product.
- Any concomitant vaccination administered in the period starting from screening up to study end.
- Prophylactic medication (*i.e.* medication administered in the absence of ANY symptom and in anticipation of a reaction to the injection). *E.g.* an anti-pyretic is considered to be prophylactic when it is given in the absence of fever and any other symptom, to prevent fever from occurring.
- Any concomitant medication/product/vaccine relevant to a SAE\* or administered at any time during the study period for the treatment of a SAE\*, or administered at any time during the study for treatment of an adverse event leading to study termination, or treatment of an adverse event requiring a medically attended visit.

*\*SAEs that are required to be reported per protocol.*

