## 9. OUTCOME MEASURES AND STATISTICAL METHODS

### 9.1 Sample Size Estimation

Since this is an open, non-comparative study that seeks to observe the impact of vaccination on the evolution of HIV disease, a sample size defined by statistical criteria is not established.

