## **12.2 Endpoint Review Committee**

The Endpoint Review Committee (ERC) will be blinded to the treatment assignments. Each endpoint case will be reviewed independently by two ERC members to confirm endpoint and severity; if their adjudications conflict, the endpoint will also be reviewed by a third member and the endpoint will be adjudicated by the majority vote. Members of the ERC will be appointed by the Study Steering Committee. Each positive laboratory result will be reviewed by the ERC. A detailed outline of ERC regulations and endpoint case criteria, in addition to the criteria defined below, will be available in the ERC charter.

Endpoints cases are defined by any of the following events:

1. A participant has an illness visit and virological confirmation (positive PCR test). PCR SARS-CoV-2 tests are permitted to be carried out at local study sites. Every effort will be made to verify positive PCR tests in a central reference laboratory.
2. A participant has an illness visit and serological confirmation of SARS-CoV-2. A positive serology test is defined by a four-fold rise or greater to N antibody titers in association with the illness.
3. A participant has illness visit and both virological and serological confirmation.
4. A participant who does not present with any symptoms (does not have any illness visits) but demonstrates seroconversion to the N antigen between the Injection and Week 52 visits.

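### The anti-N case definitions make no exception for a recorded N-containing COVID-19 vaccine given during follow-up, so as written such a vaccination can qualify as infection

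*Protocol*

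**What the plan says.** **Asymptomatic case.** The objective in the Synopsis is "Evaluate the efficacy of Ad5-nCoV in preventing asymptomatic disease of COVID-19 (confirmed by N IgG antibody on week 52 after vaccination"). Section 2.2.4 and both endpoint lists (Synopsis, Exploratory Objective Endpoints; Section 9.3.5) carry the same definition. Under Final serology the Synopsis describes the comparison: the one-year anti-N levels "will be compared to the participant's baseline levels to evaluate the exploratory efficacy analysis against asymptomatic infection". Item 4 of the case list in Section 12.2 applies to a participant with no illness visit who "demonstrates seroconversion to the N antigen between the Injection and Week 52 visits".

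**Serology-only symptomatic case.** The same objective and endpoint lists accept a four-fold anti-N rise as confirmation. The reference may be either the pre-immunization sample or a pre-symptom sample. Section 3.5 (Confirmed case) compares convalescent with acute serum, and Section 12.2, item 2, ties the rise to the illness.

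**Other vaccines.** Section 6.2 requires this to be recorded: "Any concomitant vaccination administered in the period starting from screening up to study end". Section 4.2 excludes prior coronavirus vaccination at entry and planned receipt of other vaccines within 14 days either side of study vaccination. The elimination rules in Section 6.2 say that such use does not require withdrawal and may affect only according-to-protocol evaluability. Section 1.3 gives the reason for the amendment: "The advancement of the national vaccination reduced the possibilities of access to the study under such design".

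**The concern.** Sections 6.1 and 12.2 together imply the logic of the marker: the study vaccine expresses S only, so N seroconversion should point to infection and not to the study injection. That logic fails for anyone who later receives a vaccine that itself contains N. The protocol foresees that outside vaccines may be given and collects them, yet none of its case definitions uses that information.

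The specificity of two exploratory infection endpoints is at stake. Every participant receives Ad5-nCoV and Section 9.1 calls the study open and non-comparative, so no control group would show the same false positives. Any such cases would simply be added to the infections listed among vaccinees and would make the study vaccine look less protective than it is.

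**Working it through.** The protocol states no figure to reproduce. Section 9.1 says "a sample size defined by statistical criteria is not established", and no attack rate or case count is given. The check is therefore first a reading of the rules, then an illustration resting on assumptions.

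**Step 1: does the rule capture the participant?** Take a participant with no anti-N at baseline and no illness visit, who receives a registered N-containing vaccine after Day 70 and has anti-N at Week 52.
- Section 12.2, item 4: no symptoms, N seroconversion between injection and Week 52. Met.
- Synopsis, Final serology: Week 52 anti-N above baseline. Met.
- Section 4.2: planned vaccines are barred only within 14 days of a study injection. The second injection is at Day 56, so the bar ends at Day 70. From there to Day 364 is 294 days, or 42 weeks.
- Section 6.2, elimination rules: the 14-day window has passed. The rule that applies at any time covers only investigational or non-registered products. Both rules concern according-to-protocol evaluability, not case status.

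The participant qualifies, and no listed rule removes them.

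**Step 2: the serology-only symptomatic case.**
- Pre-immunization reference: a vaccine given at any time between the first injection and the post-illness sample can supply the four-fold rise, so a later PCR-negative illness can be confirmed by it.
- Acute-to-convalescent pair: an earlier vaccine is already reflected in the acute serum. This comparison is affected only if the vaccination falls near or inside the interval between the two samples.

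**Step 3: illustration.** Input from the protocol: N = 500 (Section 3.2, "A total of 500 participants will be enrolled to receive the vaccine"). Assumed, because the documents give none of them: a = proportion truly infected and N-positive by Week 52; q = share given an N-containing vaccine in follow-up; s = share of those who become anti-N positive. Vaccination and infection are taken as independent.

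False cases = N × (1 − a) × q × s. True cases = N × a.

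With a = 10% and s = 70%, true cases = 500 × 0.10 = 50:
- q = 0: 0 false; apparent proportion 10%.
- q = 1%: 500 × 0.90 × 0.01 × 0.70 = 3.15 false; apparent 53.15/500 = 10.6%; 3.15/53.15 = 6% of counted cases false.
- q = 5%: 15.75 false; apparent 65.75/500 = 13.2%; 15.75/65.75 = 24% false.
- q = 10%: 31.5 false; apparent 81.5/500 = 16.3%; 31.5/81.5 = 39% false.

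Over s = 50–90% and a = 5–20%, false cases range over about 2–4 (q = 1%), 10–21 (q = 5%) and 20–43 (q = 10%).

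**The case against.** The strongest reply is that this is detail for other documents. Section 9.3 leaves the details of statistical methods to the SAP, and Section 12.2 says further case criteria will be in the committee charter. Neither is shown, and either may contain an exception. Every endpoint case is also adjudicated. A reader might therefore infer that outside vaccinations are, or will be, counted as infections; the documents do not establish that. What survives is narrower. The protocol itself fixes the case rule, the charter criteria are described as additional to it, and item 4 gives an adjudicator no stated ground to reject a participant who meets it.

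The trigger is also undocumented. Section 1.1 lists inactivated-virus vaccines among candidates worldwide. Section 1.3 names no product and mentions national vaccination as an obstacle to enrolment, not as something participants took. Every participant is offered two active doses, which weakens the motive to seek another vaccine. That an inactivated whole-virus vaccine raises anti-N is general immunology and is not stated in the protocol. All of this stands, and it is why no size can be asserted.

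It would also be too strong to say that any anti-N rise makes a case. The asymptomatic rule asks for seroconversion, though without a threshold. The symptomatic rule asks for a four-fold rise with illness, and paired acute and convalescent sera are largely protected.

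Finally, the endpoints are exploratory and descriptive, no formal efficacy hypothesis is tested (Section 9.3.2), and the missing comparator is the larger limitation. This bounds the importance of the point but does not remove it.

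**Conclusion.** The point holds as a gap in the stated case definitions. A participant who seroconverts to N after a recorded N-containing COVID-19 vaccine qualifies as an asymptomatic case. A symptomatic, PCR-negative one can qualify through the pre-immunization reference. The protocol neither bars a registered vaccine of this kind outside the 14-day windows nor gives it any consequence for case status.

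The possible effect is upward bias in exploratory, descriptive infection counts. Its size depends wholly on assumed uptake, anti-N response and true infection risk: none at zero uptake, and about 16 false beside 50 true cases at 5%, 70% and 10%. A reader might take the illustration as an estimate of actual contamination, or infer that a vaccine-efficacy estimate is biased by a known amount. The documents support neither: they report no uptake, and there is no comparative estimate. Primary safety and S-RBD endpoints do not use anti-N.

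**What to change.** Add one rule wherever the serological case is defined: the Synopsis (Exploratory Objectives, Final serology, Exploratory Objective Endpoints) and Sections 2.2.4, 9.3.5 and 12.2. Add it also to the Confirmed case and Endpoint case definitions in Section 3.5, to cover the paired comparison. It should state that an anti-N result drawn after recorded receipt of an N-containing COVID-19 vaccine is not evaluable for serological confirmation or for the asymptomatic endpoint. Serological follow-up ends at that vaccination date, and the affected participants are listed separately. PCR-confirmed cases count as before. The committee charter should carry the same wording.

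The cost is a short text change repeated in several places, plus shorter serological follow-up for those participants. No new data collection is needed, because outside vaccinations are already recorded to study end; the product must be identifiable from that record. Testing stored back-up aliquots drawn before the outside vaccination (Day 84 or Week 24) would recover some of the lost follow-up, but is optional.
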